6.2.6 Telephone Check-in

Study coordinators will call enrolled subjects who have completed study visit 1 twice to check in. The first time will be approximately 1 week after the first study visit and the second time 1 week before the second study visit. These telephone check-ins will 1) serve as a reminder to participants to complete their daily symptom diary, 2) remind participants to take the medication as prescribed 3) address any participant questions or concerns, and 4) remind/confirm participants’ second study visit appointment.

Participants who wish to discontinue the study medication and unenroll from the study will be directed to speak with the study PI to receive instructions for tapering off of the medication if they have not done so already.

6.27 Completion/Final Evaluation

We will attempt to schedule subjects’ Visit 2 appointments as close to the 8-week window as possible but will allow a window of several days (53-60 days). Visit 2 will be scheduled simultaneously with Visit 1 to help promote adherence to this timeline. If it is not safe for the subject to come to the lab for study Visit 2 (due to the COVID-19 pandemic), we will have the subject complete questionnaires online and schedule a video or telephone call to obtain adverse

event data, determine whether the subject benefited from the medication, and conduct the debriefing.

- Blood draw (optional) – 7.5 mL of blood will be obtained by a trained study staff member or phlebotomist. Blood will be processed to obtain RNA and plasma then frozen at -80°C for later omics analyses.
- Current medication List – will be pulled from Epic or the prior visit and verified with the subject by a study team physician.
- GERD-HRQL - a validated 11 item scale for assessing the impact of GERD symptoms on health-related quality of life⁷³.
- NIH PROMIS GERD scale – a validated 13 item instrument assessing frequency and severity of GERD symptoms over a 7 day recall period²⁶.
- GSRS: The Gastrointestinal Symptom Rating Scale is a validated 15 item instrument for measuring the severity of gastrointestinal symptoms⁷⁴. It contains 5 subscales: abdominal pain, reflux syndrome, diarrhea syndrome, indigestion syndrome, and constipation syndrome.
- Current Stress Question – 1 item self-report measure of current stress level on a scale of 0 (no stress) to 10 (extreme stress).
- Perceived Stress Scale (PSS) – a widely used 10 item measure of perceived stress that has been shown to correlate with a variety of different health outcomes⁷⁵.
- Adverse events – study staff will ask subjects if they experienced any adverse events and ask about any hospital or emergency room visits since enrollment.
- Daily symptom diary – Identical in content to the baseline symptom diary, this diary allows subjects to track the frequency and severity of 9 different GERD and dyspepsia-related symptoms on a 5 point scale as well as any medications, supplements, or other products used to help manage symptoms.
- Debriefing – a study team member will debrief with each subject regarding the two different visit types and the patient-provider interaction being studied. See Appendix F for a debriefing script.

If a subject experienced benefit taking amitriptyline or omeprazole, they will be offered a 30 day prescription so that they may continue taking the medication until they have a chance to follow-up with their PCP or gastroenterologist who can continue prescribing and monitoring the medication. If a subject did not experience any benefit and/or wishes to stop the medication, they will be instructed in how to taper off of it.

7. SAFETY ASSESSMENTS

Expected risks to subjects are as follows:

- Study questionnaires: Symptom and behavioral data collection involves virtually no risk; however, psychosocial tests or questions about symptom intensity may cause minor emotional distress. Because participants are free to stop at any time and will be reminded of this throughout the assessment process, the risk of distress is low. In our experience, such questionnaires are well-tolerated and complications are extremely rare.
- Discomfort from ECG/GSR leads and physiologic monitoring: Some participants may experience minor skin irritation due to the adhesive used to apply leads for physiologic monitoring. Subjects with known adhesive allergies will not be eligible to participate in the study. Some participants may experience psychological distress knowing that their physiology is being monitored. The physiologic monitoring will be described in the consent document and care will be taken to minimize such distress. Participants will be free to stop at any time. In general, such monitoring is well-tolerated.
- Discomfort from blood draws: some participants may have an aversion to needles, blood, and/or the drawing of blood. Blood will be drawn by trained study staff or phlebotomists and care will be taken to minimize discomfort to participants. Blood draws are generally well-tolerated, although occasionally there may be bruising or discomfort at the site. Rarely an infection can occur. The blood draw will be an optional component of the study, and if an enrolled subject consents to the blood draw and is particularly challenging to draw blood from, we cancel the blood draw and will not require a successful blood draw to be a condition of continued enrollment in the study.
- Videotaping: Some participants may experience psychological distress knowing that they are being videotaped. Participants will be free to stop at any time. In general, videotaping is generally well-tolerated.
- Amitriptyline: The most common side effects are dry mouth, sleepiness, and constipation. Less common side effects include dizziness, fatigue, headache, agitation, tremor, blurred vision, nausea, insomnia, and sexual dysfunction. Rare side effects include an allergic reaction, changes in heart conduction causing slowing or speeding up of the heart rate, serotonin syndrome, and suicidal ideation. We are prescribing low doses of this medication and have excluded those most vulnerable to adverse effects and so do not anticipate any serious adverse events. If a study subject calls with concerns about side effects, they will be directed to speak with a physician on the study team to assess their symptoms and determine whether any dose modification or further evaluation is needed. If it is deemed that the subject should stop the medication, they will be instructed in how to do so. If it is determined that they need further medical evaluation, they will be instructed what to do.
- Omeprazole: The most common side effects are headaches, abdominal pain, diarrhea, and nausea. Less common side effects include skin rash, constipation, dizziness, and back pain. Rarely someone may develop a hypersensitivity reaction, acute interstitial nephritis, lupus, or an enteric infection. Long-term use may increase the risk of

fractures, vitamin B12 deficiency, or low magnesium levels. Despite these risks, omeprazole is generally well-tolerated and available over-the-counter. If a study subject calls with concerns about side effects, they will be directed to speak with a physician on the study team to assess their symptoms and determine whether any dose modification or further evaluation is needed. If it is deemed that the subject should stop the medication, they will be instructed in how to do so. If it is determined that they need further medical evaluation, they will be instructed what to do.

- Severe GERD symptoms: It is possible that subjects may experience a flare in their GERD symptoms during the study. If a subject calls with severe GERD symptoms, he or she will be directed to speak with a study physician to discuss their symptoms and determine the best course of action. In some cases as needed antacids may be recommended for refractory symptoms. If this recommendation does not suffice, the subject may need to initiate additional medication and possibly be removed from the study.
- Deception: Subjects may experience minor psychological distress at study visit 2 when they learn that some information was withheld from them at enrollment. Based upon our experience with our prior studies, we feel this is unlikely to happen or to be problematic as we have experience conducting such debriefings and subjects generally understand why such information was withheld initially.

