3. STUDY DESIGN

Study design: Single-center, single-blind, randomized controlled trial

Primary outcome:

1. Change in the average daily GERD symptom severity score from baseline to the last week of the study in the expanded vs. standard group. GERD symptom severity is based on the sum of scores assessing the severity of daytime heartburn, nighttime heartburn, and acid reflux each on a 0-4 point scale (none, mild, moderate, severe, very severe; higher scores signify worse symptoms).

Secondary outcomes:

1. Ratio of the sum of positive correlations over the sum of negative correlations in GSR (or HRV) across patient-provider encounters for standard vs. expanded visit types and for responders vs. non-responders (those with a 50% or greater improvement in their GERD symptom severity).
2. Absolute change in GSR (or high frequency HRV signal) in patient recordings from the beginning of the study visit to the end of the study visit and correlation with subsequent change in GERD symptom severity.
3. Differences in blinded ratings of 2 minute thin slices of study visit videos from the beginning to the end of the study in supportive global impressions (e.g., engagement, relaxed, patient seems pleased/satisfied) and non-verbal behaviors (e.g., smiling) between standard and expanded visit types and correlation with subsequent change in GERD symptom severity.

Study population:

Men and women age 24-70 with heartburn symptoms 3 or more days per week not responsive to proton pump inhibitors or with known functional heartburn. We will enroll until we reach 60 completing subjects.

Study location:

University of California Davis Medical Center

Length of subject participation: 8 weeks

Length of study enrollment: 2 years

Groups:

- 1) Standard visit (n=30), modeled after an empathic, high quality conventional primary care visit.
- 2) Expanded visit (n=30), modeled after a visit with an integrative medicine provider

Randomization:

The randomization code will be generated by the study statistician as described below (sections 4.3 and 9.2). The study will be single-blinded (study providers and the research team will know what the subject is receiving but the subject will not). Randomization will be stratified based on study provider. We anticipate 5 or 6 providers each seeing 10-12 subjects (5-6 standard visits, 5-6 expanded visits).

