5.4 Adherence Assessment

Subject adherence is defined by subjects completing at least 6 out of 7 days of their daily symptom diary during the last week of the study period and taking amitriptyline

or omeprazole at least 6 out of 7 days during that week. Adherence will be assessed when subjects return their symptom diaries at their follow-up visit. For subjects who return incomplete symptom diaries, average daily symptom severity for the days completed will be calculated. If there is insufficient data to make this calculation, we will assume that symptoms are unchanged from baseline.

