7.3 Adverse Events and Serious Adverse Events

An **adverse event (AE)** is any unfavorable or unintended diagnosis, symptom, sign, syndrome or disease which either occurs during the study (having been absent at baseline), or if present at baseline, appears to worsen.

A **serious adverse event (SAE)** is any untoward medical occurrence that results in death, is life threatening, requires inpatient hospitalization or prolongation of existing hospitalization, results in persistent or significant disability/incapacity, or is a congenital anomaly.

During the follow-up visit, the study team member will specifically ask about any new or worsening symptoms in the last 8 weeks, unanticipated medical appointments, emergency room, or hospital visits.

In addition, during telephone check-ins, the study research coordinator will record any health concerns reported by subjects (not specifically solicited) and report these to the study PI. If there are any signs or symptoms of concern or that require further clarification, the study PI will contact the subject.

- Unexpected fatal or life-threatening AEs related to the intervention will be reported to the National Center for Complementary and Integrative Health (NCCIH) Program Officer within 3 business days of the investigator becoming aware of the event and to the study's Independent Safety Monitor(s) and UC Davis IRB within 5 business days of the investigator becoming aware of the event. Other serious and unexpected AEs related to the intervention will be reported within 5 business days.
- Anticipated or unrelated SAEs will be handled in a less urgent manner but will be reported to the Independent Safety Monitor(s), IRB, and other oversight organizations in accordance with their requirements and will be reported to NCCIH on an annual basis.
- All other AEs documented during the course of the trial will be reported to NCCIH and the UC Davis IRB on an annual basis by way of inclusion in the annual report and in the annual AE summary which will be provided to NCCIH and to the Independent Monitors. The Independent Safety Monitor(s) Report will state that all AEs have been reviewed (see Data Safety and Monitoring Plan).

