7.4 Reporting Procedures

Study staff and visit intervention providers will be instructed to report all adverse events (or potential AEs) to the study PI ([name]). Determination of relatedness will be made in conjunction with [name] and/or [name]. An electronic log of various types of AEs will be kept and updated by study staff.

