8. INTERVENTION DISCONTINUATION

Subjects who decline to participate in study procedures (e.g., completion of study questionnaires, physiologic monitoring, and/or video recording) will be terminated from the study without further follow-up. Any subjects who are disruptive or felt to pose a threat to study staff will also be terminated without follow-up. If a subject experiences an adverse reaction to amitriptyline or omeprazole and decides to stop taking the medication, or if a study physician deems it in the subject's best interest to stop the medication, the subject will continue to be followed for the duration of their initially planned participation (out to 8 weeks), unless the subject declines to participate further.

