9.3 Definition of Populations

For analyses including the intervention group type, we will analyze our data according to which visit intervention subjects received (standard or expanded). We do not anticipate any discrepancies between what subjects were assigned to receive by randomization and what they actually received. Study visit type will be guided by a written script that the providers will follow during the visit. The actual intervention received will also be verified by reviewing study video recordings.

The intent to treat analysis will include all randomized subjects who received a study visit intervention. The per protocol analysis will include all individuals who received a study visit intervention and completed the follow-up questionnaires at 8

weeks.

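### A subject who adds GERD medication for a severe flare but stays on study drug may be removed with no week-8 follow-up stated, so the primary score can be lost for a reason tied to the outcome (minor).

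*Combined protocol and SAP*

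**What the plan says.** The flare pathway is in the severe-symptoms item of the risk list in section 7. The subject speaks to a study physician. "In some cases as needed antacids may be recommended for refractory symptoms"; if that is not enough, "the subject may need to initiate additional medication and possibly be removed from the study". No criterion separates those removed from those kept, and nothing is said about the diary or Visit 2 after removal.

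Section 8 sets the follow-up rules. For a subject who stops amitriptyline or omeprazole after an adverse reaction, or because a study physician judges that best, "the subject will continue to be followed for the duration of their initially planned participation (out to 8 weeks"), unless the subject declines. Termination without follow-up is reserved for subjects who refuse study procedures or who are disruptive or threatening. Flare is not on that list.

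Section 5.3.3 asks subjects not to add GERD medication and monitors this through the diary and the follow-up medication review. It attaches no consequence for follow-up or analysis.

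Three further rules decide what happens to a missing score. Section 9.3: "The intent to treat analysis will include all randomized subjects who received a study visit intervention". Section 5.4, on incomplete diaries: "If there is insufficient data to make this calculation, we will assume that symptoms are unchanged from baseline". Section 3: "We will enroll until we reach 60 completing subjects".

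**The concern.** The primary analysis in section 9.5.1 is an ANCOVA on the week-8 diary score. Removal for a severe flare is triggered by the construct that this diary measures, so a score lost this way is not missing at random with respect to the outcome. The decision is left to a study physician, and section 6.2.4 says that staff know the visit type from just before the visit onward. If removals differed between arms in number or severity, the treatment difference would shift. Diary days that were never kept cannot be recovered afterwards.

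**Working it through.** **1. The plan's own yardstick.** Inputs from section 9.2: 30 per arm, 80% power, two-sided alpha 0.05, SD 1.5, 2.0 or 2.5. The minimal detectable difference (MDD) is the difference d at which a two-sample t test with 58 df and noncentrality d / (SD × √(2/30)) has 80% power. This gives 1.103, 1.471 and 1.839, matching the tabulated 1.10, 1.47 and 1.84. Section 9.2 expects an SD above the pilot's 1.5, so the larger values are relevant too.

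**2. Which flare subjects are uncovered.** Sections 7 and 8 read together:

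- Flare settles with antacids: the subject stays in, and the week-8 score is observed.
- Physician stops study drug: section 8 follows the subject to 8 weeks.
- GERD medication added, study drug continued, subject kept: the score is observed.
- GERD medication added, study drug continued, subject removed: no section provides for a week-8 diary.

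Only the last path is a gap.

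**3. What happens to that subject's score.** Section 9.3 keeps the subject in the intention-to-treat set. Section 5.4 was written for incomplete diaries, but it is the only rule available and would probably set the change to zero. Further enrolment to 60 completers (section 3) adds a subject but does not restore the lost value.

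**4. How much that could matter.** Let k be the number removed in each arm and W their true change from baseline at week 8 (positive = worse). Taking the difference as standard minus expanded at week 8, the no-change rule understates it by

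shift = (k_std × W_std − k_exp × W_exp) / 30.

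The documents give neither k nor W, so **every k and W below is an assumption**:

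- 3 v 1, W = +1: 2/30 × 1 = 0.067 (6.1%, 4.5%, 3.6% of the three MDDs).
- 3 v 1, W = +3: 2/30 × 3 = 0.200 (18.2%, 13.6%, 10.9%).
- 2 v 1, W = +1: 1/30 × 1 = 0.033 (3.0%, 2.3%, 1.8%).
- 2 v 1, W = +3: 1/30 × 3 = 0.100 (9.1%, 6.8%, 5.4%).
- Added medication would have brought a 2.5-point improvement (W = −2.5): 3 v 1 gives −0.167 and 2 v 1 gives −0.083. The sign reverses, and the difference is overstated.
- 2 v 2 with W = +3 standard and +1 expanded: (6 − 2)/30 = 0.133.
- Equal numbers and equal W: 0.

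More removals in the expanded arm reverse each sign. If removed subjects are replaced to reach 30 completers per arm, the 3 v 1 multiplier falls from 2/30 = 0.0667 to 3/33 − 1/31 = 0.0587. A simulated baseline-adjusted ANCOVA (30 per arm, residual SD 2.0, 4,000 runs) returned the 3 v 1 and 2 v 1 shifts to within 0.001. That confirms the arithmetic; it says nothing about how often removal would occur.

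**The case against.** The case against is strong on consequence. The sentence sits in a list of expected risks, while follow-up is governed by section 8, which covers physician-directed stopping of study drug and does not list flare as grounds for termination. Harm needs a chain: the subject calls, antacids fail, medication is added, study drug continues, the subject is still removed, and such losses differ between arms. No link has a stated rate. A flare treated during the 8 weeks need not leave the last-week score worse than baseline. The illustrative shifts are small beside the standard error of the difference, 2.0 × √(2/30) = 0.52 at SD 2.0. The separate safety monitoring plan (Appendix G) is not available here and could contain a criterion. All of this stands, and it is why the priority is minor. It does not close the last path in step 2.

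A reader might infer more than the text supports:

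- *Every subject removed for a flare is lost to follow-up.* Section 8 says otherwise for anyone a physician takes off study drug.
- *The flare would vanish from the record.* Section 7.3 counts a condition as an adverse event when, "if present at baseline, appears to worsen"; section 7.4 adds that "An electronic log of various types of AEs will be kept and updated by study staff", and section 7.5 follows events by phone or medical record. What these do not supply is the seven-day diary score.
- *The subject drops out of the primary analysis.* Section 9.3 retains the subject.
- *The trial is biased against, or towards, the expanded visit.* The direction depends on unstated counts and on whether the added medication works.

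**Conclusion.** The concern holds in a narrow form. Sections 7 and 8 leave one type of subject without stated outcome follow-up: one who adds GERD medication for a severe flare, stays on study drug and is removed. The score would be lost for an outcome-related reason and probably replaced by no change from baseline, which could be too favourable (an uncontrolled flare) or too unfavourable (a successful rescue). The affected group may be very small. Under the assumed counts the shift runs from −0.17 to +0.20 points, and it is zero when removals and their severity balance; the documents do not allow any of these cases to be called likely. The MDD table in section 9.2 is unaffected. The conclusion rests on the visible text and on section 5.4 being applied to a removed subject. How post-rescue scores should enter the analysis is a choice of estimand, not an error, and is not part of this finding. Minor priority, worth doing because it costs almost nothing.

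**What to change.** 1. In section 7, replace the removal option at the end of the flare item with a statement that the subject continues the diary and attends Visit 2 to 8 weeks, whatever GERD medication is added. The clinical decision stays with the study physician.
2. In section 8, extend the existing follow-up sentence to adding GERD medication for any reason, unless the subject declines or meets the termination criteria already listed there.

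The observed week-8 score then enters the intention-to-treat ANCOVA as already planned.

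The cost is wording in two sections. The downside is that some week-8 scores will reflect rescue medication and may look better than the untreated flare would have. An optional sensitivity analysis can show how much that matters, identifying these subjects from the diary medication entries and the Visit 2 medication review, both already collected.
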